7.2 Centre data

7.2.1 Staffing and equipment

The overall number of staff members (radiologists, radiographers, nurses) as well as the different type of staff, the overall number of scanners and the type of scanners, the number of procedures during the study period, the type of decision and the decision makers, and the challenges will be analysed for all sites and by country.

7.2.2 User satisfaction

Packaging satisfaction, injector satisfaction will be analysed overall, by country and by GBCA. In addition, the reason for ratings will be given for the different satisfaction categories. These will be ordered by frequency.

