3 STUDY METHODS

3.1 Study design and plan description

This is a prospective, multi-center observational study.

It is planned to enroll up to 5400 patients from 7 countries and 14 sites.

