3.2.3 Centre data

- Number of available scanners in centre (MRI, CT, ultrasound, PET-PET/CT, PET/MR, SPECT, X-ray)
- Number of procedures performed in the centre (liver-specific MR, Non_CE MR, CE-MRI, CE-MRA, CT, ultrasound, PET-PET/CT-PET/MR, SPECT, X-ray, other) during the study period
- Number of staff members (radiologists, radiographers, nurses)
- Decision for use of a specific contrast medium (individual decision, collective decision)
- Decision maker for use of specific contrast medium (Head of radiology department, radiologist, specialty physician, pharmacist, manager [non-clinician], other)
- Challenges faced by radiology department
- User satisfaction with GBCA packaging and injectors
 - for each GBCA
 - Satisfaction with GBCA packaging (could be improved, o.k., excellent/particularly good)
 - Satisfaction with injector (could be improved, o.k., excellent/particularly good)

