5.8 Statistical significance (p-values)

A p-value of <0.05 will be declared as statistically significant.

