7 STATISTICAL METHODS

All continuous variables will be summarized using the following descriptive statistics: n (non-missing sample size), mean, standard deviation, median, minimum and maximum. The frequency and percentages (based on the non-missing sample size) will be reported for categorical measures. Data that will be listed will be sorted by country, site and subject.

For the comparison of endpoints in stratified analyses (e.g. by country, by GBCA etc.) explorative statistical tests will be applied (ANOVA for continuous endpoints, Chi-Square tests for categorical endpoints) if feasible.

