Table	8.8	Precision of the diagnostic criteria by GBCA
Table	8.9	Categories of diagnostic question
Table	8.10	Categories of diagnostic question by site
Table	8.11	Categories of diagnostic question by specialty
Table	8.12	Categories of diagnostic question by GBCA
Figure	8.13	Bar chart of mean change in radiological diagnosis by quality of referral notes
Figure	8.14	Bar chart of mean change in increase of confidence by quality of referral notes
Table	8.15	Quality of CE-MRI and CE-MRA
Table	8.16	Quality of CE-MRI and CE-MRA by age
Table	8.17	Quality of CE-MRI and CE-MRA by country
Table	8.18	Quality of CE-MRI and CE-MRA by site
Table	8.19	Quality of CE-MRI and CE-MRA by GBCA
Figure	8.20	Bar chart of mean quality of image by change in radiological diagnosis
Figure	8.21	Bar chart of mean quality of image by change in confidence for the diagnosis
Table	9.1	Staffing equipment
Table	9.2	Staffing equipment by country
Table	10.1	User satisfaction
Table	10.2	User satisfaction by country
Table	10.3	User satisfaction by GBCA
Table	11.1.1	Number of patients with adverse events by SOC and PT
Table	11.1.2	Number of patients with serious adverse events by SOC and PT
Table	11.1.3	Number of patients with adverse events by causality, SOC and PT
Table	11.1.4	Number of patients with adverse events by treatment, SOC and PT
Table	11.1.5	Number of patients with adverse events by severity, SOC and PT
Table	11.1.6	Number of patients with adverse events by time to onset, SOC and PT
Table	11.2.1	Number of patients with adverse events by site, SOC and PT
Table	11.2.2	Number of patients with serious adverse events by site, SOC and PT
Table	11.2.3	Number of patients with adverse events by site, causality, SOC and PT
Table	11.2.4	Number of patients with adverse events by site, treatment, SOC and PT
Table	11.2.5	Number of patients with adverse events by site, severity, SOC and PT
Table	11.2.6	Number of patients with adverse events by site, time to onset, SOC and PT
Table	11.3.1	Number of patients with adverse events by site, SOC and PT
Table	11.3.2	Number of patients with serious adverse events by country, SOC and PT
Table	11.3.3	Number of patients with adverse events by country, causality, SOC and PT
Table	11.3.4	Number of patients with adverse events by country, treatment, SOC and PT
Table	11.3.5	Number of patients with adverse events by country, severity, SOC and PT
Table	11.3.6	Number of patients with adverse events by country, time to onset, SOC and PT

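### A centre's satisfaction ratings of several GBCAs are related, but the SAP's default chi-square for the by-GBCA and by-country tables would treat them as independent

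*SAP*

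**What the plan says.** SAP section 3.2.3 lists "User satisfaction with GBCA packaging and injectors" among the centre data and asks for it separately for each GBCA. The scale has three ordered levels, given for packaging as "Satisfaction with GBCA packaging (could be improved, o.k., excellent/particularly good", and the injector item uses the same levels. Section 3.1 sets the number of centres: "It is planned to enroll up to 5400 patients from 7 countries and 14 sites".

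Section 7.2.2 gives the analysis: "Packaging satisfaction, injector satisfaction will be analysed overall, by country and by GBCA". Appendix 1 lists Tables 10.1 (overall), 10.2 (by country) and 10.3, the last titled "User satisfaction by GBCA".

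The only rule for comparing strata is in section 7. It opens "For the comparison of endpoints in stratified analyses (e.g. by country, by GBCA etc" and continues that "explorative statistical tests will be applied (ANOVA for continuous endpoints, Chi-Square tests for categorical endpoints) if feasible". Section 5.8 adds: "A p-value of <0.05 will be declared as statistically significant". No paired, stratified or clustered method appears anywhere, and section 5.6 on multi-center studies is marked as not applicable. Percentages are based on the non-missing sample size, but for satisfaction the SAP does not say whether that counts centres or ratings.

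**The concern.** The chi-square test assumes that every rating is independent of every other. Here a centre that uses three GBCAs contributes three ratings, and a centre that is generally easy or hard to please will shift all three. Ignoring this has different effects in different tables.

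- **Table 10.3 (by GBCA).** A centre's ratings are spread over the groups being compared. The test ignores the matching, uses too large a variance, and may miss a brand difference.
- **Table 10.2 (by country).** All of a centre's ratings fall in one group. The test uses too small a variance and may declare a country difference that is not there.
- **Table 10.1 (overall).** Nothing is compared, but if ratings are the unit, a four-brand centre counts four times and a one-brand centre once.

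Separately, if centres rate different brands, the brand percentages in Table 10.3 carry the leniency of the centres that happen to use each brand. This affects the descriptive result whether or not a test is run.

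**Working it through.** The SAP gives no power, effect size or correlation for this endpoint, so there is no figure of its own to reproduce. From the SAP come 14 centres, 7 countries, three ordered levels, the chi-square test and the 0.05 threshold. The number of GBCAs rated per centre, the within-centre correlation ρ, the category split and the size of a brand difference are assumptions.

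**1. Direction.** Take a latent rating with variance 1 and correlation ρ between two ratings from the same centre.

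- Two brands, both rated by n centres: the variance of the mean difference is 2(1−ρ)/n, while an independent-groups test uses 2/n. The ratio is 1−ρ, or 0.5 at ρ = 0.5, so the test is conservative.
- A country with c centres, each rating k brands: the variance of the country mean is [1+(k−1)ρ]/(ck), while the test uses 1/(ck). At ρ = 0.5 the ratio is 1.5, 2.0 and 2.5 for k = 2, 3 and 4, so the test is anti-conservative.

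**2. Table 10.3, full overlap.** Simulation with 6,000 replicates per setting: 14 centres all rating two brands, latent normal cut at −0.84 and 0.25 (about 20/40/40%), brand difference 0.8 SD. The Pearson chi-square on the 2×3 table is compared with the centre-stratified Cochran-Mantel-Haenszel (CMH) mean-score statistic (Σd)²/Σd² on 1 df, where d is the within-centre score difference.

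| ρ | Chi-square power | CMH power | Chi-square type I error |
|---|---|---|---|
| 0 | 31% | 37% | not reported |
| 0.3 | 27% | 44% | 3.8% |
| 0.5 | 26% | 52% | 2.2% |
| 0.7 | 24% | 66% | 1.3% |

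The CMH type I error at ρ = 0.5 is 4.3%. With 10 centres at ρ = 0.5, power is 14% against 35%. Not all of the gap is due to matching. At ρ = 0.5 an unpaired mean-score test reaches 38%, so of the 52 − 26 = 26 points, 38 − 26 = 12 come from using the category order and 52 − 38 = 14 from the matching.

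**3. Table 10.3, other patterns.** A second simulation used 1,000 runs per setting, a 20/50/30% split, one brand shifted by 1 SD, and a within-centre permutation test as comparator. Power at ρ = 0.3 / 0.5 / 0.7:

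| Pattern | Chi-square | Within centre |
|---|---|---|
| 2 brands, all rated everywhere | 44/43/42% | 52/58/74% |
| 3 brands, all rated everywhere | 42/41/35% | 63/78/88% |
| 3 brands, 2 per centre | 30/25/24% | 31/34/41% |
| 4 brands, 2 per centre | 17/19/16% | 19/20/22% |
| 5 brands, 2 per centre | 13/13/12% | 12/14/14% |

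In the last two rows the difference runs from −1 to 6 points.

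**4. Table 10.2.** With 7 countries of 2 centres each, ρ = 0.5 and no true difference, the simulated type I error of the nominal 5% chi-square is about 15%, 31% and 46% with 2, 3 and 4 brands per centre. This agrees with the variance ratios in step 1.

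**5. Brand mixed with centre leniency.** Suppose there is no true brand difference and a baseline of 30% in the top category (latent cut 0.524). A centre more lenient by 0.5 SD has top-category probability 1−Φ(0.024) = 0.490; one more lenient by 1 SD has 1−Φ(−0.476) = 0.683. Let 4 lenient centres rate only A, 4 rate only B, and 6 rate both:

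- 0.5 SD: A = (4×0.490 + 6×0.300)/10 = 37.6%, B = 30%.
- 1 SD: A = (4×0.683 + 6×0.300)/10 = 45.3%, B = 30%.

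With no overlap (7 centres each), A is 49% or 68% against 30%. If all 14 centres rate both brands, the bias is zero.

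**The case against.** The best counter-argument is that no chi-square may ever be run. Section 7.2.2 is worded descriptively, and section 7 calls the tests explorative and conditional on feasibility. By the usual rule of thumb (no more than 20% of cells with expected count below 5), the tables are too sparse. With 14 ratings per brand and 20% in the lowest level, the expected count there is 14×0.20 = 2.8, so 2 of 6 cells (33%) already fall below 5. In simulation over 98% of such tables broke the rule. By country it is worse: even with 4 brands per centre, 8 ratings per country give at most 8×0.40 = 3.2 per cell. This stands, and it is why the point cannot say that Table 10.3 will be tested this way. But the SAP does not define feasible, and omitting the test cures neither the leniency problem nor the undefined denominator.

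A reader might also infer more than the SAP supports:

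- **That the test loses half its power.** This holds only for two brands rated by every centre at ρ of about 0.5.
- **That the error is conservative throughout.** It is the reverse by country.
- **That low power and leniency mixing occur together.** Full overlap gives the first without the second, no overlap gives the second without the first, and only partial overlap gives both.
- **That one person rates all brands at a centre.** Section 3.2.3 does not say who completes the form.
- **That this is the only user-side comparison of Clariscan.** Radiologists' image quality and confidence ratings are also analysed by GBCA (section 7.1.8, Tables 8.4 and 8.19).

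Finally, the stakes are low. The study is descriptive, has no a priori hypothesis, and does not name satisfaction in its objectives.

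**Conclusion.** The point holds as a minor one. Ratings are collected per centre for each GBCA, and the SAP's only comparison rule treats them as independent and makes no provision for centre.

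For Table 10.3 the test, if run, is conservative and may miss brand differences, provided that brands overlap within centres and ratings correlate positively. The size runs from a substantial power loss when every centre rates the same two or three brands to almost none with four or five brands and two per centre. For Table 10.2 the test, if run, has a type I error well above 5%. The brand percentages can also be distorted by centre leniency when overlap is incomplete.

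All these sizes rest on assumed correlation, category split, brand effect and brands per centre; the by-country figures also assume two centres in each country. The SAP fixes none of these, so the figures show what could happen and are not predictions for this study.

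**What to change.** Amend section 7.2.2 as follows.

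1. State that the section 7 chi-square does not apply to Tables 10.1-10.3.
2. For Table 10.3, compare GBCAs within centre with the CMH mean-score test stratified by centre, in an exact or permutation version because the numbers are small. Show the number of centres rating each GBCA. For Clariscan against each other brand rated by the same centre, show how many centres rated it higher, equal or lower. These counts still serve descriptively if no test is run.
3. Present Tables 10.1 and 10.2 without a test, either stating the number of centres and of ratings or weighting each rating by 1/(number of GBCAs rated by that centre).

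This costs some SAP wording and a change to the table programming, with no new data. Centres rating a single brand do not contribute to the test, though they stay in the frequencies. The exact version has limits of its own: in a two-sided sign test, 6 centres to 0 gives p = 2×0.5⁶ = 0.031, but 5 to 0 gives 2×0.5⁵ = 0.063. The descriptive counts should therefore be the main result.

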7.3 Adverse events

Analysis of safety will be based on the safety population (SAF).

The number and frequency of patients with adverse events and serious adverse events will be analysed overall, by age group (SAF), by history of allergy (HISALP), by GFR rate (GFRP), by site (CSP) by country (CSP), by specialty (SPP) and by GBCA (GBCAP) by MedDRA SOC and PT.

The number and frequency of adverse events will also be analysed for the subgroups given above stratified by causality, treatment, severity and onset of the adverse event.

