3.2.1.3 Medical summary

- Diagnosis to which MR scan has been indicated
- Question to be answered with the use of CE-MR
- Secondary diagnosis
- Reason for using a contrast medium (border delineation of pathology, overall morphological characterization of pathology/lesion, overall increase in resolution of images required, confirmation of opinion/diagnosis, for comparison with non-contrast enhanced images, angiography or myocardial assessment, standard procedure for this diagnostic question, other)
- Specific reason why the GBCA was used
- Comorbidities (none, allergy, diabetes mellitus, heart failure, hepatic impairment, hypertension, neurologic symptom, renal impairment, autoimmune disease, malignancy/cancer, other)
 - Allergy status for patients with allergies (bronchial asthma, eczema, food allergy, urticaria, previous history of allergy to other contrast media [unknown media, Iodine-based media, Gadolinium-based media, ultrasound media, other media])
 - Renal status eGFR for patients with renal impairment (< 15, 15-30, 31-60, > 60 mL/min/m², impaired [exact eGFR unknown], unimpaired [exact eGFR n/a])
 - If renal status < 60 mL/min/m²: status of renal replacement for the compromised kidney(s) (renal replacement – dialysis, renal transplant, no replacement)
- Pre-medications (none, steroids, anti-histamines, other)
- Concomitant medications (no co-medication, chemotherapy/active treatment for malignancy, radiotherapy, anti-hypertensives, diabetic medications, heart failure treatment, nephrotoxic medication [antibiotics, iodinated agents, oncological drugs, immunosuppressants, other], other)
- Source of funding for the scan (self-funded [n/a, full, partially], paid by personal/hospital insurance, reimbursed by the state)

- If funding = insurance or reimbursed, what is being paid for (contrast media, procedure, procedure including contrast media)

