6 ANALYSIS SETS

The allocation of subjects to analysis sets will be determined by the sponsor and the CRO on a per-subject basis immediately before data base lock.

Full eligible population (FEP)

The FEP population consists of all screened subjects, both successful and failed screens.

Full included population (FIP)

The FIP population consists of all successful screens.

Safety population (SAF)

The SAF population consists of all patients with a documented MRI/MRA procedure.

Population by country/site (CSP)

The CSP population consists of all successful screens in with known country/site.

Population by GBCA type (GBCAP)

The GBCA population consists of all subjects with known GBCA brand type.

Population by speciality (SPP)

The SPP population consists of all subjects examined for an ailment with known speciality.

Population by GFR rate (GFRP)

The GFR population consists of all subjects with known range of GFR rate.

Population by History of allergy (HISALP)

The history of allergy population consists of all subjects with known history of allergy status.

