Table	11.4.1	Number of patients with adverse events by site, SOC and PT
Table	11.4.2	Number of patients with serious adverse events by specialty, SOC and PT
Table	11.4.3	Number of patients with adverse events by specialty, causality, SOC and PT
Table	11.4.4	Number of patients with adverse events by specialty, treatment, SOC and PT
Table	11.4.5	Number of patients with adverse events by specialty, severity, SOC and PT
Table	11.4.6	Number of patients with adverse events by specialty, time to onset, SOC and PT
Table	11.5.1	Number of patients with adverse events by site, SOC and PT
Table	11.5.2	Number of patients with serious adverse events by GBCA, SOC and PT

Table	11.5.3	Number of patients with adverse events by GBCA, causality, SOC and PT
Table	11.5.4	Number of patients with adverse events by GBCA, treatment, SOC and PT
Table	11.5.5	Number of patients with adverse events by GBCA, severity, SOC and PT
Table	11.5.6	Number of patients with adverse events by GBCA, time to onset, SOC and PT
Table	11.6.1	Number of patients with adverse events and serious adverse events by severity
Table	11.6.2	Number of patients with adverse events and serious adverse events by GFR rate
Table	11.6.3	Number of patients with adverse events and serious adverse events by history of allergy

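### Adverse events may be compared between contrast agents by an unadjusted test, with no account of allergy history or pre-medication, although both are collected

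*SAP*

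**What the plan says.** The secondary objective (SAP section 2.1) covers the safety profile of GBCAs, Clariscan included. Section 7.3 lists the AE subgroups one by one: age group, then "by history of allergy (HISALP), by GFR rate (GFRP), by site (CSP) by country (CSP), by specialty (SPP) and by GBCA (GBCAP"). The only second-level split is for the "subgroups given above stratified by causality, treatment, severity and onset of the adverse event".

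Appendix 1 follows this pattern. The 11.5 series has titles such as "Number of patients with adverse events by GBCA, causality, SOC and PT". Table 11.5.1 is titled by site, apparently a copying slip; I read it as by GBCA. Allergy history has a single AE table, 11.6.3: "Number of patients with adverse events and serious adverse events by history of allergy". No title crosses GBCA with allergy history, and none uses pre-medication.

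The data exist. Section 3.2.1.3 records "previous history of allergy to other contrast media [unknown media, Iodine-based media, Gadolinium-based media, ultrasound media, other media"] and "Pre-medications (none, steroids, anti-histamines, other"). Section 6 defines an allergy population: "The history of allergy population consists of all subjects with known history of allergy status".

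Three general sections bear on the point. Section 5.3 lists the stratifiers for endpoints, and neither allergy history nor pre-medication is among them. Section 7 provides exploratory chi-square tests for categorical endpoints in stratified analyses, naming GBCA as an example, where feasible. Section 5.8 declares p<0.05 significant, and section 5.7 makes no multiplicity adjustment.

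**The concern.** Agents are not assigned at random here. Whoever chooses the agent may take earlier reactions into account, and some patients are pre-medicated. Both could plausibly change the chance of an AE and could differ between brands. The plan treats allergy history as relevant to AEs, since it gives it a population and a table, but leaves it out where brands are set side by side.

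A brand that receives more patients with earlier reactions could show a raised crude AE rate. A brand whose patients are more often pre-medicated could show a lowered one. Either could occur with no difference between agents. At stake is whether a crude difference, possibly labelled significant, is read as a property of Clariscan or of another agent.

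**Working it through.** **1. What the plan crosses with GBCA in the AE output**

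| Factor | Collected? | Crossed with GBCA for AEs? |
|---|---|---|
| Causality, severity, onset | yes | yes (11.5.3, 11.5.5, 11.5.6) |
| Treatment | named in 7.3 | yes (11.5.4) |
| Allergy history | yes | no (11.6.3 stands alone) |
| Earlier contrast-medium reaction | yes, by class of medium | no |
| Pre-medication | yes | no, and in no AE table |

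Treatment does not supply the missing cross: Table 11.5.4 names it beside GBCA, so it is a different factor.

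**2. Size under assumed inputs**

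The SAP states no AE rate, allergy share or brand size, so there is no figure to reproduce and every input here is assumed. Suppose no true brand effect, an AE risk of 0.5% without allergy history, and allergy shares of 15% on brand B and 5% on brand A.

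Crude risk = share × risk if allergic + (1 − share) × risk if not.

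| Risk if allergic | Brand B | Brand A | Crude ratio B/A |
|---|---|---|---|
| 3% | 0.15×3% + 0.85×0.5% = 0.875% | 0.05×3% + 0.95×0.5% = 0.625% | 1.40 |
| 2% | 0.725% | 0.575% | 1.26 |
| 1.5% | 0.650% | 0.550% | 1.18 |

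Within each allergy stratum the ratio is 1.00 by construction. With equal shares the crude ratio is also 1.00.

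**3. Direction**

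Take the 3% row and suppose, as a limiting case, that pre-medication removed all the excess risk on brand B only. Its crude risk becomes 0.5%, and the ratio is 0.5/0.625 = 0.80. The sign therefore depends on facts the SAP does not give.

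**4. A wider grid, for earlier contrast reactors alone**

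Crude risk = r0 × (1 + p × (RR − 1)), where r0 is the risk without an earlier reaction, p the share of earlier reactors and RR their relative risk (3, 5 or 8).

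- p of 2% versus 5%: ratio 1.06 to 1.18.
- p of 2% versus 10%: ratio 1.15 to 1.49.
- p of 1% versus 15%: ratio 1.27 to 1.92.

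**5. How often the crude test would mislead**

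Assume two equal brands. With 2700 each (all 5400 planned patients on two brands), the 1.40 case gives 2700×0.875% = 23.6 against 2700×0.625% = 16.9 expected patients with an AE. The 95% interval around 1.40 is about 0.75 to 2.6, and a two-sided 0.05 test declares a difference in about 19% of studies instead of 5%. With 1000 each it is 8.75 against 6.25, an interval of about 0.5 to 3.9, and about 10%. The 1.26 and 1.18 cases give about 6% to 11% over both sizes. In the step 4 grid the figure reaches 83%, but only with 1% versus 15% earlier reactors, RR 8, r0 of 1% and 2700 per brand.

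**6. How far the data can be split**

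Expected AE patients among the allergic in the 3% case are 2700×0.15×3% = 12.2 and 2700×0.05×3% = 4.1, or 4.5 and 1.5 with 1000 per brand. That can support overall counts by stratum, but not a further division by MedDRA system organ class (SOC) and preferred term (PT).

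**The case against.** **The study is descriptive.** Section 1.2 says that no prior hypothesis is tested, the objective is to look at a safety profile rather than compare agents, and section 7.3 promises only counts and frequencies. This has weight, but sections 7 and 5.8 together permit a significance test of AEs by GBCA. Calling it exploratory does not remove confounding, and nothing in the SAP says that the brand rates are not for comparison.

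**The mechanism is not in the SAP.** This stands. A reader might infer that patients who reacted to another agent are moved to Clariscan under pre-medication, so that its crude rate is biased upwards or merely mirrors its case mix. The SAP does not say that anyone is switched, or that Clariscan receives them. Earlier reactions are recorded by class of medium, not by brand, so a switch could not be seen in that item. Section 3.2.3 also allows the agent to be chosen collectively or by a department head, pharmacist or manager. Where that happens, site may be the larger confounder.

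**Imbalance is already shown.** Section 7.1.4 and Table 4.3 give comorbidities, allergy among them, and pre-medications by GBCA. That is a real partial safeguard. But AEs are not in that table, and section 7.1.4 does not say that the allergy details, which hold the earlier contrast reactions, are given by GBCA.

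**The bias is small against chance.** In the assumed examples the interval is wide and includes 1. That limits the urgency. It is also a reason not to rest any statement on the crude test.

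**Conclusion.** The gap is real and moderate. The plan permits an unadjusted AE comparison between brands in a non-randomised study and leaves out two recorded patient factors that may bear on both the choice of agent and the AE risk. A crude brand rate may therefore reflect in part whom the brand was given to.

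The size rests wholly on assumed inputs. The 15% versus 5% examples give spurious ratios of about 1.2 to 1.4 before any effect of pre-medication, which could bring the ratio below 1; no imbalance gives no bias. The SAP does not support saying that Clariscan's rate is biased, or in which direction. It supports only that the planned output could not tell an agent effect from patient selection on these factors.

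**What to change.** In section 7.3 and Appendix 1:

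- Add one table of overall AE and serious AE counts, not by SOC or PT, by GBCA within strata of allergy history (none / other allergy / earlier contrast-medium reaction) and pre-medication (yes / no). The three levels are needed because the recorded allergy status also covers asthma, eczema, food allergy and urticaria.
- Where counts allow, replace the crude chi-square comparison of AEs by GBCA with a Mantel-Haenszel risk ratio and 95% confidence interval for Clariscan versus other GBCAs over these strata. Add site as a further stratifier in a sensitivity analysis.
- State that the by-GBCA AE tables (11.5.x) are descriptive and not comparative.

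All variables are already collected, so the cost is one table and one estimate. The downsides are sparse strata, of which those without events contribute nothing to the pooled ratio, and a wider interval than the crude comparison. The risk ratio also adds a comparative estimate that the SAP does not now name. If counts turn out too low, the table and the statement alone still close most of the gap.

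### SAP 7.3 bases safety on SAF but assigns AE tables by site, country, GFR and allergy history to sets not defined within SAF; separately, Appendix 1 mistitles three AE tables and lists none by age group

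*SAP*

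**What the plan says.** Section 7.3 opens with a general rule: "Analysis of safety will be based on the safety population (SAF"). The next sentence lists the breakdowns and puts a set in brackets after each. First come "by age group (SAF), by history of allergy (HISALP), by GFR rate (GFRP"), then "by site (CSP) by country (CSP), by specialty (SPP) and by GBCA (GBCAP) by MedDRA SOC and PT". SAF is named only for age group.

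Section 6 defines the sets:

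- SAF: "The SAF population consists of all patients with a documented MRI/MRA procedure".
- CSP: "The CSP population consists of all successful screens in with known country/site".
- SPP: "The SPP population consists of all subjects examined for an ailment with known speciality".
- GBCAP, GFRP and HISALP: subjects whose GBCA brand, GFR range or allergy history, respectively, is known.

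None of the last five is described as a subset of SAF.

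Section 8 refers to Appendix 1 for the tables to be generated. There, Tables 11.2.1, 11.3.1, 11.4.1 and 11.5.1 share one title: "Number of patients with adverse events by site, SOC and PT". The remaining tables of the 11.3, 11.4 and 11.5 blocks are by country, specialty and GBCA. Table 11.6.1 reads "Number of patients with adverse events and serious adverse events by severity", 11.6.2 is by GFR rate and 11.6.3 by history of allergy. No table in the 11 series is by age group.

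**The concern.** Section 2.1 makes the safety profile of GBCAs, including Clariscan, part of the secondary objective, so readers will compare AE percentages across subgroups and with the overall figure. That comparison is clean only if every percentage comes from the same patients. A programmer who follows the brackets in 7.3 would use SAF for the overall and age-group tables, everyone who passed screening for site and country, and all subjects with a known status for GFR and allergy history. A patient without a recorded procedure could then enter some denominators and not others.

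The table list is a second, independent problem. Read by title, it repeats the by-site AE table three times, has no all-AE table by country, specialty or GBCA, and omits the age-group breakdown that 7.3 plans.

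**Working it through.** The SAP gives no AE rate and no calculated sample size (section 4), so there is no figure to reproduce. The check is of the text, with one illustration.

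**Step 1: does each set used in 7.3 lie within SAF?**

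| AE breakdown (7.3) | Set named | Recorded MRI/MRA required by section 6? | In practice within SAF? |
|---|---|---|---|
| Age group | SAF | Yes | Yes |
| Site, country | CSP | No; passing screening is enough | Not assured |
| GFR | GFRP | No; known range is enough | Not assured |
| Allergy history | HISALP | No; known status is enough | Not assured |
| Specialty | SPP | Not by name, but the subject was examined | Very likely |
| GBCA | GBCAP | Not by name | Very likely: 3.2.1.5 records brand under the MRI and MRA details |

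The clear departures are therefore CSP, GFRP and HISALP.

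**Step 2: would an unscanned patient drop out as missing?** Section 7 bases percentages on non-missing values. The AE variables in 3.2.1.8 describe events (verbatim, seriousness, onset, causality, severity), and the list shows no yes/no item for any AE. A patient with no AE record would therefore probably count as having had none, and would stay in the denominator.

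**Step 3: direction and form of the effect.** Assume that SAF lies within CSP and that all AEs occur in SAF. Then

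AE rate on CSP = AE rate on SAF × (number in SAF ÷ number in CSP).

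The ratio does not depend on the AE rate. To show scale only, take 5400 in CSP (the enrolment ceiling in 3.1), an AE rate of about 1%, and a share of patients without a recorded procedure of 1%, 5% or 10%. The AE rate and the shares are assumptions; the SAP gives neither.

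| Assumed share | SAF n | Patients with AE | Rate on SAF | Rate on CSP | Ratio |
|---|---|---|---|---|---|
| 1% | 5346 | 53 | 53/5346 = 0.991% | 53/5400 = 0.981% | 0.99 |
| 5% | 5130 | 51 | 51/5130 = 0.994% | 51/5400 = 0.944% | 0.95 |
| 10% | 4860 | 49 | 49/4860 = 1.008% | 49/5400 = 0.907% | 0.90 |

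The absolute shift runs from about 0.01 to 0.10 percentage points. With a share of zero the ratio is 1. GFRP and HISALP also drop patients of unknown status, so their rates can differ from the overall SAF rate in either direction and no single factor applies.

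**Step 4: table titles against 7.3.**

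| Table | Title says | Rest of block | Reading |
|---|---|---|---|
| 11.3.1 | by site | country (11.3.2 to 11.3.6) | mistitled |
| 11.4.1 | by site | specialty (11.4.2 to 11.4.6) | mistitled |
| 11.5.1 | by site | GBCA (11.5.2 to 11.5.6) | mistitled |
| none | – | – | age-group AE table planned in 7.3 but not listed |

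**The case against.** The best defence is that the opening sentence of 7.3 governs everything after it, so that the bracketed sets are only flags for patients in SAF whose characteristic is known. That is a sensible reading and may be what was meant. But the SAP never states the intersection, and SAF in brackets after age group suggests that each bracket names the set to be analysed. The text supports both readings, so a clarifying line is needed.

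It is also fair to say that subgroups with a known characteristic need not add up to SAF even when formed within it, because missing values are not replaced (5.5). The failure to add up is therefore not in itself an error; showing the number unknown makes it visible.

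A reader might infer more than the document supports:

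- *That AE rates by GBCA and specialty are materially diluted.* Brand is recorded with the scan details, and SPP covers subjects who were examined.
- *That uninjected patients count as exposed.* SAF does not require contrast, although 3.2.1.8 times AE onset from injection. Whether any enrolled patient had no contrast depends on eligibility rules in the protocol, which is not at hand. Much of the SAP points to a contrast-enhanced cohort: the reason for contrast, brand and volume, and the CE-MRI and CE-MRA outcomes.
- *That the AE table by GBCA is missing.* Its place in the GBCA block and the requirement in 7.3 point to a title error.
- *That Table 11.6.1 duplicates 11.1.5.* Table 11.1.5 is by severity, SOC and PT. Table 11.6.1 covers AEs and serious AEs by severity without SOC and PT. It may be a mistitled age-group table, but the document does not show that.
- *That the title errors cause the denominator problem.* That problem comes from the set definitions alone.

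**Conclusion.** The point holds for two separate defects.

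First, 7.3 names SAF for safety and then assigns the site, country, GFR and allergy-history breakdowns to sets that section 6 does not place within SAF. On a literal reading, these rates use a different denominator from the overall rate. The size cannot be known from the SAP. The illustrated ratios of 0.99 to 0.90 follow from assumed shares of 1% to 10%, with SAF inside CSP and all AEs in SAF, and are not an estimate. In a descriptive study the absolute effect may well be small.

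Second, three AE table titles contradict their blocks, and the age-group table that 7.3 plans is not listed. This is a matter of correct output and does not bias any rate.

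Both deserve correction because AE rates serve a stated objective and the correction is nearly free.

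**What to change.** - State in 7.3 that every AE table uses SAF, that each subgroup consists of the SAF patients whose characteristic is known, and that the number unknown is shown beside it.
- Retitle Table 11.3.1 by country, 11.4.1 by specialty and 11.5.1 by GBCA.
- Add a table of AEs and serious AEs by age group. Keep 11.6.1 as listed.
- Check the protocol. If it allows scans without contrast, also limit SAF to patients given a GBCA. Do not make a completed brand or volume field the test, since that would remove injected patients, and possibly their AEs, only because a field is blank.

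The cost is a few lines of SAP text, minor reprogramming of population flags and one added table. AE rates may become slightly less favourable. Section 6 allocates subjects to sets immediately before database lock, so the change should be made before then.
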